### 4.4 Open Label Extension Sets

For the OLE phase, several different analysis sets will be defined.

1. The open label extension (OLE) set will consist of all patients enrolled into the OLE phase of the study who receive at least one dose of open label study drug.
2. Octreotide capsule patients from the DPC period who enrolled into the OLE phase and received at least one dose of open label study drug (OLE-OCT)
3. Octreotide capsule patients from the DPC period, who were classified as treatment responders based on the primary endpoint, at the end of the DPC period, and who enrolled into the OLE phase and received at least one dose of open label study drug (OLE-OCT-RESP).

## 5 Analysis Endpoints

### 5.1 Efficacy Endpoints

#### 5.1.1 Primary Efficacy Endpoint

The proportion of patients who maintain their biochemical response at the end of the DPC period. Maintenance of response will be defined by using the average IGF-1 level of the last 2 available assessments [REDACTED] in the DPC period [REDACTED].

[REDACTED]. If the average IGF-1 is  $\leq 1 \times \text{ULN}$ , a patient will be classified as a responder (i.e., maintained their biochemical response). If the average IGF-1 is  $> 1 \times \text{ULN}$ , a

patient will be classified as a non-responder. Patients who discontinue study medication during the DPC period for any reason will be classified as non-responders for the primary analysis, regardless of their IGF-1 values.

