#### **6.10.4 Prohibited Concomitant Medication**

Women taking oral contraception containing levonorgestrel are advised to switch to another oral contraceptive or barrier method.

Investigational therapy for the treatment of acromegaly are prohibited during the course of the study.

Parenteral SRLs or dopamine agonists, GH antagonists are prohibited while the patient is treated with study medication (octreotide capsules/placebo).

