## 4 Analysis Sets

### 4.1 Full Analysis Set

The Full Analysis Set (FAS) is defined as all randomized patients. This population will serve as the primary efficacy analysis population for the DPC period of the study. Patients will be included in the group to which they were randomized.

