### 4.2 Per-Protocol Set

The per-protocol (PP) set will consist of all subjects in the FAS set who were compliant with study medication, and do not have any major protocol violation (e.g., administration of a prohibited concomitant medication, violation of inclusion/exclusion criteria, non-compliance with study medication). Protocol violations that will exclude a subject from the PP set will be identified prior to breaking the blind. This set will be used to assess efficacy and will provide support to the primary analyses with the FAS set.

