#### **6.3.2 Outliers**

All reported values will be included in the analyses.

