### **6.4.2 Protocol Violations and Treatment Compliance**

For the FAS set, all major protocol violations (e.g., administration of a prohibited concomitant medication, violation of inclusion/exclusion criteria) will be listed by site, including action taken (e.g. discontinuing a subject), if any.

A tabular summary of all major protocol violations will be provided by site, and overall, by treatment group and overall. Major protocol violations will be classified as:

- Violations of inclusion and exclusion criteria
- Receiving the wrong study medication
- Non-compliance with study medication. A patient is defined as non-compliant if the patient took < 75% of the study medication.
- Taking a prohibited medication or receiving a prohibited therapy
- Other

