## 6.8 Efficacy Analyses

### 6.8.1 Primary Endpoint Analysis

The primary efficacy analysis will estimate the proportion of responders, based on the primary endpoint, at the end of the DPC period, within the octreotide capsules and placebo arms. An assessment of superiority will be made using an exact logistic regression model, with covariates for treatment, baseline SRL dose (low vs mid or high) and baseline IGF-1 level ( $<$  median vs  $\geq$  median). If the two-sided p-value is  $< 0.05$ , octreotide capsules will be declared superior to placebo. The adjusted proportions, difference in proportions and associated two-sided 95% confidence intervals will be reported. In addition, the odds ratio and two-sided 95% confidence interval (CI) will be reported. The FAS will be the primary population used for this analysis, with the PP population used as a supportive analysis.

Patients who discontinue study medication during the DPC period for any reason will be classified as non-responders for the primary analysis, regardless of their IGF-1 values. [REDACTED]

To assess the impact of missing data on the primary endpoint, several sensitivity analyses will be conducted using multiple imputation.

[REDACTED]

The primary endpoint analysis results will be reported overall and by sub-groups (region, age, gender and race). The same statistical methodology applied to the primary endpoint analysis will be used for analyzing the primary endpoint by each sub-group.

Randomization, in theory, should provide balance of all baseline characteristics, between the two treatment groups. At the conclusion of the study, if there is an imbalance in any baseline characteristics felt to be clinically meaningful, the effect of this imbalance on the primary endpoint will be evaluated through inclusion of covariates for these characteristics into the primary model above. These analyses will be considered sensitivity analyses to investigate the robustness of the primary analysis.

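### In the visible text, a patient who adds a prohibited acromegaly drug but stays on capsules is classified by IGF-1 or GH values alone, and counts as a responder in the FAS if those values are in range

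*SAP*

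**What the plan says.** **Primary endpoint.** SAP 5.1.1 averages the last two available IGF-1 assessments in the DPC period. If the average is at or below 1 x ULN, "a patient will be classified as a responder (i.e., maintained their biochemical response"). One override is visible: "Patients who discontinue study medication during the DPC period for any reason will be classified as non-responders for the primary analysis". SAP 6.8.1 repeats that these patients "will be classified as non-responders for the primary analysis, regardless of their IGF-1 values", and Protocol 2.2.1 gives the same rule. Text is redacted inside the definition in Protocol 2.2.1 and SAP 5.1.1, and directly after the rule in SAP 6.8.1.

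**Prohibited drugs.** Protocol 6.10.4: "Parenteral SRLs or dopamine agonists, GH antagonists are prohibited while the patient is treated with study medication".

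**Consequence of a breach.** SAP 6.4.2 lists "Taking a prohibited medication or receiving a prohibited therapy" among the major violations to be listed and tabulated. SAP 4.2 excludes patients from the per-protocol set for violations such as "administration of a prohibited concomitant medication, violation of inclusion/exclusion criteria, non-compliance with study medication". The primary population is unaffected: "The Full Analysis Set (FAS) is defined as all randomized patients". The Outliers section (SAP 6.3.2) adds that "All reported values will be included in the analyses".

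**Secondary endpoints.** SAP 5.1.2 shows no redaction in items 1 to 4. GH non-response is forced only by discontinuing treatment. Definitions (A), (B) and (C) of both time-to-loss endpoints deal only with patients who stop treatment early.

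**The concern.** The endpoint is meant to show control maintained by the assigned capsule, and the plan already treats stopping the capsule as failure whatever the IGF-1 value. A patient who keeps taking capsules and adds another drug that lowers GH or IGF-1 raises the same attribution problem, yet the visible rule credits the result to the randomised arm.

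The situation is foreseeable. Rescue requires IGF-1 of at least 1.3 x ULN together with worsening signs or symptoms, on two consecutive assessments, after at least two weeks on four capsules a day (Protocol 3, SAP 3). The dose is fixed after Week 24 (Protocol 6.2). A patient between 1 and 1.3 x ULN, or above 1.3 x ULN without symptoms, does not meet the rescue criteria and may stay uncontrolled in either arm while other treatments exist outside the trial. The documents do not say how often a patient in that position would take one.

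At stake are the primary comparison and the GH and time-to-loss endpoints, which sit in the fixed testing sequence of SAP 6.3.5.

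**Working it through.** The point concerns a classification rule, so the main check is to follow one patient through it. The design response rates and the power table are redacted in Protocol 8.1 and SAP 3.2, so there is no planning figure to reproduce.

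**Step 1: the patient.** Randomised, still taking capsules at Week 36, has added a drug prohibited by Protocol 6.10.4.

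- *In the primary population?* Yes. The FAS is all randomised patients (SAP 4.1).
- *Does the visible override apply?* No. It needs discontinuation of study medication. Protocol 4.6 lists non-compliance as a reason for which a patient may discontinue, and SAP 6.4.2 records the action taken if there was any. Neither makes stopping automatic.
- *Are the IGF-1 values set aside?* No visible rule does so.
- *Primary result.* Responder if the average is at or below 1 x ULN, non-responder otherwise.
- *GH response.* Classified on the Week 36 mean GH alone, if GH was below 2.5 ng/mL at Screening.
- *Time to loss.* If the added drug holds IGF-1 at or below the threshold, there is no event and the patient is censored at Week 36. Definitions (A) to (C) do not apply because treatment was not stopped.
- *Missing-data sensitivity analyses.* Not a remedy. SAP 6.8.1 describes multiple imputation for missing data, and a value measured on a prohibited drug is not missing.
- *Per-protocol analysis.* Removes the patient instead of counting a failure, and removes patients with other violations too.

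**Step 2: the rescued patient, for contrast.** Protocol 4.6.1 describes SRL rescue for patients who have discontinued study medication. That patient is already a primary non-responder, a GH non-responder and an event under definition (A). The gap does not touch protocol rescue.

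**Step 3: size.** About 50 patients at 1:1 (SAP 3.2) gives 50 / 2 = 25 per arm. One patient is 1 / 25 = 4 percentage points.

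**Step 4: illustration on assumed counts.** Two-sided Fisher exact p-values, 25 per arm, as a stand-in for the planned exact logistic regression. The counts are invented.

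| Octreotide v placebo responders | p |
|---|---|
| 15 v 6 | 0.021 |
| 15 v 7 (one extra placebo responder) | 0.045 |
| 15 v 8 (two extra) | 0.088 |
| 13 v 5 | 0.038 |
| 12 v 5 (one octreotide responder rescored) | 0.072 |
| 15 v 7 | 0.045 |
| 14 v 7 (one octreotide responder rescored) | 0.085 |

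The first three rows show prohibited use on placebo hiding an effect. The last four show prohibited use on octreotide creating a nominally significant result. One or two patients matter only when the result is already near 0.05.

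**The case against.** **Redaction.** The strongest objection is that the primary rule is blacked out where further conditions could sit: inside the definition in Protocol 2.2.1 and SAP 5.1.1, and right after the discontinuation rule in SAP 6.8.1. A reader might infer that the primary rule covers nothing but stopping medication. The documents do not support that as a statement of fact, because redacted text is not absent text. This stands, and it limits the primary-endpoint point to the visible wording. It does not reach the GH and time-to-loss definitions, where nothing is redacted.

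**Foreseeable use is already handled.** SRL rescue follows discontinuation and is non-response. A reader might infer that rescued patients can be counted as successes; Protocol 4.6.1 read with SAP 5.1.1 shows otherwise. What remains is a protocol deviation, and it would not be hidden: violations are tabulated by arm (SAP 6.4.2), concomitant medication is summarised by arm (SAP 6.7), SRL re-initiation is shown by time point and arm (SAP 6.9.1.1), and a per-protocol analysis is planned. This narrows the scope. Reporting a deviation still does not decide how the patient counts in the primary result.

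**No frequency, invented counts.** Correct. Two such patients on placebo would be 2 / 25 = 8% of that arm, and nothing in the documents says even one is expected.

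**Observed outcomes for all randomised patients are a legitimate choice.** True in general. This plan, though, has already chosen to count loss of the assigned treatment as failure, and the added-drug case is an exception to its own logic.

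**A rule triggered by any exposure would be too broad.** This stands. A brief exposure early in the DPC period should not override normal IGF-1 at Weeks 34 and 36.

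**Conclusion.** The point holds in limited form. On the visible rules, a FAS patient who adds a prohibited acromegaly drug and stays on capsules is classified by IGF-1 or GH alone, and is a responder when the value is in range. For GH response and both time-to-loss endpoints this rests on unredacted text. For the primary endpoint it depends on the redacted text not covering the case.

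Three stronger readings are not supported. Such a patient is not a responder automatically: the average IGF-1 must be at or below 1 x ULN. The gap does not favour octreotide by construction: use on octreotide inflates the difference and use on placebo dilutes it. And endpoint 4 is not shown to be wrong if it leaves out dopamine agonists and GH antagonists, since Protocol 4.6.1 and SAP 3 describe rescue as the injectable SRL used before Screening.

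The size is about 4 points in one arm per affected patient, assuming about 25 per arm. The number of such patients is unknown. It is worth settling before unblinding because the rule is cheap to write then and open to challenge afterwards.

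**What to change.** 1. The sponsor confirms whether the redacted text in Protocol 2.2.1, SAP 5.1.1 and SAP 6.8.1 already covers prohibited acromegaly medication taken on capsules. If so, carry the same rule into SAP 5.1.2 and 6.8.2.
2. If not, add to SAP 5.1.1, 5.1.2, 6.8.1 and 6.8.2, before unblinding, a rule such as: *IGF-1 or GH values obtained under the influence of a parenteral SRL, dopamine agonist or GH antagonist taken during capsule treatment cannot support a response; a patient whose endpoint assessment includes such a value is a non-responder.* The sponsor defines the exposure window before the assessment for each drug class, and affected patients are identified under blind. Classify these patients as non-responders instead of setting the value to missing. Otherwise the last two available assessments could slide back to earlier values, and SAP 6.8.2 would impute the Week 36 GH.
3. Count the start of such a drug as an event in definition (A) of both time-to-loss endpoints.
4. Report the observed-value classification as a sensitivity analysis.
5. Leave endpoint 4 as SRL rescue, and tabulate other prohibited acromegaly drugs separately by arm.

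Cost: a few lines in the SAP and one protocol amendment line, since SAP 1 requires changes to the primary endpoint to go through an amendment. Observed response may fall slightly in either arm. The change concerns analysis only and alters no patient's treatment.

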### 5.1.2 Secondary Efficacy Endpoints

1. Proportion of patients who maintain GH response (i.e., GH < 2.5 ng/mL) at week 36, out of those who were responders (i.e., GH < 2.5 ng/mL) on SRL injections at Screening. GH response will be defined using the mean integrated GH value, based on 5 assessments, 30 minutes apart. Patients who discontinue treatment during the DPC period for any reason will be classified as non-responders for the GH response analysis, regardless of their GH values.
2. Time to loss of response: Loss of response is defined as the earliest time when the IGF-1 of 2 consecutive visits is  $> 1 \times \text{ULN}$ , after the patient is treated for at least 2 weeks with 4 capsules per day. The date time of the earliest of the 2 consecutive measurements will be used. To account for patients who prematurely discontinue treatment prior to meeting these criteria, three different approaches will be used (i.e., this endpoint will be defined in three different ways). The three different definitions that will be used are as follows; (A) they will be counted as having had an event (i.e., met the criteria) at the time of treatment discontinuation; (B) they will be censored at the time of their last available assessment, when the patient was known to have not lost response. If there is no post-baseline assessment for response status, the patient will be censored with a time to loss of response of 0; and (C) they will not be censored, but evaluated for response based on the data collected after discontinuation (i.e., as long as the patient is known to be a responder regardless of adherence to treatment. For all three approaches patients who complete the study without meeting these criteria will be censored at their last study visit during the DPC period (i.e., week 36). Although 3 different approaches will be used, only the first approach will be used with respect to determining success. The other 2 approaches will not be considered in the multiplicity adjustment and are considered exploratory.
3. Time to loss of response: Loss of response is defined as the earliest time when the IGF-1 of 2 consecutive visits is  $> 1.3 \times \text{ULN}$ , after the patient is treated for at least 2 weeks with 4 capsules per day. The date time of the earliest of the 2 consecutive measurements will be used. To account for patients who prematurely discontinue treatment prior to meeting these criteria, three different approaches will be used (i.e., this endpoint will be defined in three different ways). The three different definitions that will be used are the same as those outlined for the endpoint above (endpoint #4). Patients who complete the study without meeting these criteria will be censored at their last study visit during the DPC period (i.e., week 36). Although 3 different approaches will be used, only the first approach will be used with respect to determining success. The other 2 approaches will not be considered in the multiplicity adjustment and are considered exploratory.

4. Proportion of patients who begin rescue treatment prior to and including week 36. The denominator for each group will be all patients randomized to that group. The numerator will be those who start rescue treatment prior to and including week 36.

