### **Common Gastrointestinal Adverse Events**

In the previous Phase 3 Study (CH-ACM-01), GI symptoms were among the most commonly reported AEs. These AEs were generally transient and declined with time (median duration was 13 days). Most were mild to moderate in intensity, and occurred during the first two months. There was no dose relationship and most resolved with treatment continuation.

In patients who develop abdominal symptoms (e.g., nausea, vomiting, abdominal pain or diarrhea), common GI illnesses should be excluded (e.g., gastroenteritis, cholestasis, etc.), and treated accordingly. If symptoms are mild to moderate in intensity and patient is able to tolerate oral medications, consideration should be given to treating the patient symptomatically with anti-emetics or anti-diarrheals to determine if patient's GI symptoms will resolve on therapy. Patients who have severe or persistent symptoms or who cannot tolerate food/fluids should be discontinued.

Of note, a phase 1 study showed no interaction between loperamide and oral octreotide capsules.

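### Read literally, exploratory approach C for time to loss of response cannot record a loss in a patient who stops before two weeks on 4 capsules a day, and scores that patient event-free to Week 36 if follow-up continues

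*SAP*

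**What the plan says.** SAP 5.1.2 item 2 defines loss of response as IGF-1 above 1 x ULN at two visits in a row, counted only "after the patient is treated for at least 2 weeks with 4 capsules per day". Item 3 does the same at 1.3 x ULN. For patients who stop treatment before meeting the definition there are three approaches:

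- **A:** "they will be counted as having had an event (i.e., met the criteria) at the time of treatment discontinuation". Only this approach decides success.
- **B:** "they will be censored at the time of their last available assessment, when the patient was known to have not lost response", or at time 0 if there is no post-baseline assessment.
- **C:** "they will not be censored, but evaluated for response based on the data collected after discontinuation", with the unclosed remark "as long as the patient is known to be a responder regardless of adherence to treatment".

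For all three, "patients who complete the study without meeting these criteria will be censored at their last study visit during the DPC period". B and C are labelled exploratory and sit outside the multiplicity adjustment.

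Item 3 imports the approaches by reference: "The three different definitions that will be used are the same as those outlined for the endpoint above (endpoint #4". Endpoint 4 is the rescue proportion and has no such approaches; the endpoint meant is number 2.

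Protocol 6.2 starts dosing at 2 capsules a day and allows stepwise escalation through Week 24, so a patient can stop below 4 capsules. Protocol 4.6.1 and SAP 3 ask that patients who stop be followed to Week 36.

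**The concern.** C is the version that looks at what happens to IGF-1 after treatment stops. The event it looks for still contains a treatment-exposure condition that a patient off drug can no longer satisfy. Someone who stops on 2 or 3 capsules, and whose IGF-1 then rises and stays high, does not meet the definition and falls under the Week 36 censoring rule. An off-drug loss becomes event-free follow-up.

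Approach A counts every stop as an event, so a reader will naturally turn to B and C to see how far the result depends on that choice. If C turns off-drug losses into event-free time, it cannot answer that question. Two programmers working from the same text could also score the same patient in opposite ways.

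There are two related gaps. C says that stoppers are not censored, which leaves those who leave the study without a score. B's censoring date has no stated on-treatment limit, although SAP 6.9 does state one for the DPC safety analyses.

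**Working it through.** The visible text gives no power, event count or hazard ratio for this endpoint, and the sample-size table is blacked out, so there is no plan figure to reproduce. The check has two parts.

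**1. Scoring two constructed patients on the scheduled visits (Weeks 4 to 36)**

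*Patient 1* stops at Week 8 on 2 capsules a day; IGF-1 is above 1 x ULN from Week 12 on. *Patient 2* takes 4 capsules from Week 14 and stops at Week 18; IGF-1 is above 1 x ULN from Week 20 on. Both stay in follow-up.

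| Rule | Patient 1 | Patient 2 |
|---|---|---|
| A | event, Week 8 | event, Week 18 |
| B, on-treatment assessments only | censored, Week 8 | censored, Week 16 |
| B, all assessments, 4-capsule condition kept | censored, Week 36 | censored, Week 16 |
| C, 4-capsule condition kept | censored, Week 36 | event, Week 20 |
| C, 4-capsule condition waived off drug | event, Week 12 | event, Week 20 |

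The readings of C differ only for Patient 1, so the problem is confined to patients who stop before completing two weeks on 4 capsules. Patients stopping under the pre-defined withdrawal criteria have already had those two weeks and are not affected.

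**2. Illustrative effect on the comparison**

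From the documents: about 50 patients randomized 1:1, so 25 per arm (SAP 3.2); log-rank test (SAP 6.8.2); two-sided 5% level (SAP 6.3.5).

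Assumed:
- The probability of loss is 0.35 on octreotide and 0.80 on placebo.
- Early stoppers in either arm lose response off drug with probability 0.80.
- Stops fall at Week 4, 8 or 12, below 4 capsules.
- Everyone stays in follow-up.

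With *d* early stoppers in an arm and loss probability *p* among the others, expected events are:

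- condition kept: (25 − d) × p
- condition waived: (25 − d) × p + d × 0.80

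For 5 octreotide and 2 placebo stoppers:
- Octreotide: 20 × 0.35 = 7.0 kept; 7.0 + 4.0 = 11.0 waived. Event-free: 18/25 = 72% against 14/25 = 56%.
- Placebo: 23 × 0.80 = 18.4 kept; 18.4 + 1.6 = 20.0 waived. Event-free: 6.6/25 = 26.4% against 5/25 = 20%.
- Difference between arms: 45.6 points kept, 36.0 points waived.

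For 2 octreotide and 5 placebo stoppers:
- Octreotide: 23 × 0.35 = 8.05 kept (67.8% event-free); 8.05 + 1.6 = 9.65 waived (61.4%).
- Placebo: 20 × 0.80 = 16.0 kept (36%); 16.0 + 4.0 = 20.0 waived (20%).
- Difference between arms: 31.8 points kept, 41.4 points waived.

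Share of simulated trials in which the log-rank statistic (O − E)²/V exceeds 3.84, with 500 trials per row (Monte Carlo standard error at most √(0.25/500) = 0.022):

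| Early stoppers, octreotide / placebo | C, kept | C, waived | A |
|---|---|---|---|
| 0 / 0 | 0.89 | 0.89 | 0.89 |
| 2 / 2 | 0.85 | 0.83 | 0.82 |
| 5 / 2 | 0.92 | 0.67 | 0.53 |
| 2 / 5 | 0.64 | 0.87 | 0.93 |
| 5 / 5 | 0.73 | 0.66 | 0.66 |

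Keeping the condition favours whichever arm has more early low-dose stops. With equal numbers the effect is small.

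**The case against.** **C may already waive the condition.** The remark "as long as the patient is known to be a responder regardless of adherence to treatment" can be read that way, since the 4-capsule condition is itself about treatment taken. This stands in part: it would be too strong to say that C can never record such a loss. But the remark sits in an unfinished parenthesis about who is known to be a responder. It does not restate the event, and the Week 36 censoring rule refers back to the unchanged criteria. The literal coding and the apparent purpose still give opposite scores.

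**B is not defective in the same way.** A reader might infer that B shares the fault. The documents do not support that. B is a censoring rule, so recording no loss after the stop is its design. Only C mentions data collected after discontinuation, which suggests that B ends at the stop. B reaches Week 36 only if off-drug assessments count and a patient with repeated high values is still regarded as not having lost response. What stands is that the cut-off is unstated.

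**The direction of bias is not known.** It is tempting to say that octreotide gains, because Protocol 7.6 says of GI events in the earlier phase 3 study: "Most were mild to moderate in intensity, and occurred during the first two months". The same paragraph says that they were generally transient and that most resolved with continued treatment. That study was open-label and baseline-controlled (Protocol 1.3.2.2), so it gives no octreotide-versus-placebo stopping rate. The placebo capsules here contain the same permeability enhancer (Protocol synopsis), and placebo patients have come off effective injections. Either arm could have more early stops.

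**No confirmatory conclusion is at stake.** This stands. Reading B and C as checks on A is a reasonable inference, but the SAP does not call them that. Text following the secondary analyses in SAP 6.8.2 is blacked out, so other sensitivity analyses cannot be excluded.

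**Not every stopper reaches Week 36.** This also stands. Protocol 4.7 foresees loss to follow-up and withdrawn consent; for those patients the fault in C is the missing rule.

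**Conclusion.** The point holds for approach C, in items 2 and 3. As literally written, a patient who stops before completing two weeks on 4 capsules a day and remains in follow-up is scored event-free to Week 36 whatever the off-drug IGF-1 shows. That defeats the evident aim of C. The missing rule for stoppers who leave the study, the unstated cut-off in B and the wrong cross-reference in item 3 are lesser gaps in the same text.

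The size is illustrative. Under the assumed rates, the Week 36 difference between arms is overstated by 45.6 − 36.0 = 9.6 points with 5 octreotide and 2 placebo early stoppers, and understated by 41.4 − 31.8 = 9.6 points with 2 and 5. These figures rest on assumed loss probabilities, stopping numbers and complete follow-up, none of which the documents give. They show that the written rule can move the exploratory result either way; they do not predict a bias toward octreotide.

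Approach A and the fixed testing order are untouched. This should be corrected before unblinding, but it does not threaten the trial's confirmatory claims.

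**What to change.** In SAP 5.1.2, items 2 and 3:

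- **C:** After the last blinded dose, drop the 4-capsule condition. Loss is then dated at the first of two consecutive IGF-1 values above 1 x ULN (item 3: above 1.3 x ULN), using all data to Week 36. State how a pair of values on either side of the last dose is scored. State that values on restarted injectable SRL are included, because the analysis ignores adherence, and flag those patients. Censor stoppers who leave the study at their last IGF-1.
- **B:** As a clarification, censor at the last IGF-1 on or before the last blinded dose.
- **Item 3:** Change the reference from endpoint 4 to endpoint 2.

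The cost is a few sentences and small programming changes. No new data are needed, because IGF-1 is already scheduled to Week 36 after stopping. The exploratory B and C results may shift in either direction. Approach A, the testing order, dosing and rescue all stay as they are.
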